#### 4.2.1.2. Additional considerations

#### 4.2.1.2.1. Analysis of solicited events

The analysis of solicited events will be performed on Solicited Safety Set.

Grading or actual temperature/redness and swelling will be captured in the eDiary as per a modified grading of symptoms based on the FDA toxicity grading guidance for industry [Food and Drug Administration, 2007] with Grades 3 and 4 combined and swelling evaluated using the actual measurement only. Analysis by grade will use the maximum grade from Day 1 to Day 7 post vaccination.

When solicited AE data entered by the participant are incorrect, data collected by study investigator/staff on eDiary Follow-up Assessment form in Subject Case Report Forms will be used in the summaries if available.

The duration of solicited AEs of any grade will be summarized by treatment. The start date is the first day during the 7-day solicitation period with the symptom at grade > 0 while the stop date is the last day with the symptom at grade > 0 in or beyond the solicited period. In addition, the duration for specific grade(s) for each symptom defined as the number of days in the report period (i.e. from Day 1 to Day 7) with grade above or equal to specific grade will be summarized by treatment.

Duration in days of solicited administration site and systemic events will be listed. Prolonged solicited AEs that continue beyond Day 7 will be identified using a flag in listing of AEs. The derivation rule of duration in days for solicited events is detailed in section 6.2.3.8.

## 4.2.1.2.2. Analysis of unsolicited events

The analysis of unsolicited events will be performed on Exposed Set.

# 4.2.1.2.3. Combined solicited events and unsolicited events excluding serious AEs

The combined analysis of solicited and unsolicited events will be performed on the Exposed Set. A listing of participants with all combined solicited and unsolicited adverse events will be provided.

Solicited adverse events will be coded by MedDRA.

For clintrial.gov posting purposes, a summary of combined solicited and unsolicited adverse events excluding serious AEs will be produced by System Organ Class and preferred terms and according to occurrence of each event.

## 4.2.1.3. Adverse Events of Special Interest

The analysis of adverse events of special interest will be performed on Exposed Set.

For adverse events of special interest (AESI) collected up to study conclusion (M6), the following will be considered for the purpose of analyses:

- pIMDs
- Anaphylaxis or severe hypersensitivity reactions within 24 hours after study intervention administration
- Pericarditis and myocarditis.
- Virologically confirmed COVID-19 cases (Protocol Section 8.4.4.2.2)

The summary of event characteristics will be provided for each AESI as well as any potential immune-mediated diseases (pIMDs), including number and percentage of participants with any event. In addition, summary will be provided by relationship to study intervention, maximum grade/severity, outcome, and the action taken. The worst-case approach will be applied at participant level for the maximum grade/severity, i.e., a participant will only be counted once as the worst case from all the events experienced by the participant.

The percentage of participants with at least 1 report of SAE (any, related, fatal and fatal related), and with at least 1 report of AESI respectively, classified by the MedDRA PT and SOC and reported from dosing up to study end and from D1 to D30 post-dose will be tabulated with exact 95% CI.

In the AESI/SAE summaries, a participant with 2 or more AEs within the same SOC or PT level but different relationship will be counted only once in the level using the related incident.

## 4.3. Secondary Endpoint(s) Analyses

## 4.3.1. Safety

#### 4.3.1.1. Analysis of safety and reactogenicity planned in the protocol

The analysis of secondary safety endpoints will be performed on the Exposed Set.

Secondary Safety Endpoints	Statistical Analysis Methods	
MAAEs; SAEs; AESIs up to study conclusion (M6).	The number and percentage with exact 95% CI of participants reporting MAAEs, SAEs, and AESIs after the dose up to study conclusion (Month 6), as classified by the MedDRA SOC and PT, will be tabulated by treatment group. The same tabulation will be performed for causally related MAAEs, SAEs and AESIs during this period. The detailed listings of SAEs, AESIs and COVID-19 cases will also be produced. The number and percentage with exact 95% CI of participants reporting AEs/SAEs leading to withdrawal from the study will be tabulated.	

## 4.3.2. Immunogenicity

#### 4.3.2.1. Analysis of immunogenicity planned in the protocol

The analysis of the secondary immunogenicity endpoints will be performed on the PPS. The descriptive summary will consist in the number of results available (N), standard deviation, median, interquartile, minimum, and maximum, GMT or GMR, and associated 95% CIs. For the analysis of immunogenicity, missing or non-evaluable measurements will not be replaced. Therefore, a participant will be excluded from an analysis if all measurements are missing or non-evaluable.

If more than 10% of participants with BA.5 immunogenicity data at Day 15 are eliminated from any of the PPS in any treatment group, a sensitivity analysis will be carried out using the Exposed Set.

Secondary Immunogenicity Endpoints	Statistical Analysis Methods
Neutralizing titer against pseudovirus bearing S protein from vaccine encoded SARS-CoV-2 and WT strains at each collection timepoint (D1, D15, D31, M6).	Neutralizing titer (GMT) against pseudovirus bearing S protein from vaccine encoded SARS-CoV-2 and WT strains will be tabulated with 95% CI at baseline and each post vaccination visit by treatment. The 95% CI will be calculated based on the t-distribution of the log- transformed value of GMT, then back-transformed to the original scale for presentation with the assumption that log-transformed concentration is normally distributed with variance specific to each treatment group. Bar charts (including 95% CIs) of GMT in log10 scale at
	each visit by treatment will be provided. At each post vaccination timepoint, the adjusted GMTs of neutralizing titer, with their 95% CI, will be obtained using an ANCOVA model on log10 transformed titers with treatment group as a fixed factor, and log10 transformed Day 1 baseline value as a covariable.
	Once Part B data are available, Part A and Part B data will be pooled together for model based analyses. When pooled, the study part will be added as a fixed factor and adjusted GMT will be estimated under Part A condition. Groups common in Part A and Part B will be combined as one group respectively for the pooled analysis. Outputs will be displayed by 3 $\mu$ g, 10 $\mu$ g, 30 $\mu$ g, 100 $\mu$ g, and pooled placebo.
	Listing of neutralizing titers sorted by treatment and participant number will be provided.
GMR from baseline (D1) of neutralizing titer against pseudovirus bearing S protein from vaccine encoded SARS-CoV-2 and WT strains at each collection timepoint.	GMR from baseline of neutralizing titer against pseudovirus bearing S protein from vaccine encoded SARS-CoV-2 and WT strains will be tabulated with 95% CI at each post vaccination visit by treatment. The 95% CI will be calculated based on the t-distribution of the log-transformed fold rise value for GMR, then back- transformed to the original scale for presentation. Bar charts (including 95% Cls) of GMR in log2 scale at
	each post vaccination visit by treatment will be provided. At each post vaccination timepoint, the adjusted GMRs from baseline of neutralizing titer, with their 95% CI, will be obtained using an ANCOVA on log10 transformed

Secondary Immunogenicity Endpoints	Statistical Analysis Methods
	titers with treatment group as a fixed factor, and log10 transformed Day 1 baseline value as a covariable. Once Part B data are available, Part A and Part B data will be pooled together for model based analyses. When pooled, the study part will be added as a fixed factor and adjusted GMR will be estimated under Part A condition. Groups common in Part A and Part B will be combined as one group respectively for the pooled analysis. Outputs will be displayed by 3 µg, 10 µg, 30 µg, 100 µg, and pooled placebo.
	In addition, the similar ANCOVA model for GMR from baseline will be performed to further evaluate the linear dose effect, using dose level as a continuous variable.
Vaccine response rate based on neutralizing titers against vaccine encoded SARS-CoV-2 and WT strains at each collection timepoint.	The number and percentage with exact 95% CI of participants with vaccine responses of at least a 2, 4, and 8 fold increases from Day 1 baseline, with their exact 95% CI will be tabulated by treatment and visit.

The following SAS code will be used to calculate GMT/GMR from baseline, where LOGVAL is the log10 transformed GMT/GMR values at each post vaccination point, and Base is log10 transformed pre-dose GMT value. The analyses will be performed on PPS only.

```
Proc sort data = study; by group step; run; /** group will be sorted with order of Placebo, 3, 10, 30, 100***/;
```

```
proc MIXED data=study;
```

```
class group (ref='Placebo') step (ref='1'); /**step='1' indicates Part B, base=log pre-vaccination titer**/;
model LOGVAL = BASE group step/ solution noint;
```

	-	
estimate 'Placebo'	base X	group 0 0 0 0 1 step 1 0/ cl;
estimate '3'	base X	group 1 0 0 0 0 step 1 0/ cl;
estimate '10'	base X	group 0 1 0 0 0 step 1 0/ cl;
estimate '30'	base X	group 0 0 1 0 0 step 1 0/ cl;
estimate '100'	base X	group 0 0 0 1 0 step 1 0/ cl;
de output actimatac=a	stmenolin	

ods output estimates=estmrnalin;

quit;

```
where X is GMT at pre-dose across groups for Part A.
```

The following SAS code will be used to further evaluate the linear dose effect on GMR from baseline of neutralizing titer against pseudovirus bearing S protein from vaccine encoded SARS-CoV-2 and WT strains, where LOGVAL is the log10 transformed GMR values at each post vaccination point, and Base is log10 transformed pre-dose titer value. The analyses will be performed on PPS only.

```
proc MIXED data=study;
```

class step (ref='1'); /**step='1' indicates Part B, base=log pre-vaccination titer**/;			
model LOGVAL = BASE dose step/ solution;			
estimate	'Placebo'	intercept 1 base X dose 0	step 1 0/ cl;
estimate	'3'	intercept 1 base X dose 3	step 1 0/ cl;;
estimate	'10'	intercept 1 base X dose 10	step 1 0/ CL;
estimate	'30'	intercept 1 base X dose 30	step 1 0/ CL;
estimate	'100'	intercept 1 base X dose 100	step 1 0/ CL;
ods output estimates=estmrnalin;			
quit;			
where X is GMT at pre-dose across groups for Part A.			

Geometric mean ratios (GMRs) will be computed at each sampling timepoint after dosing versus baseline (D1). The GMRs and 95% Cis will be constructed by exponentiating (base 10) the means of within-participant differences between log-transformed titers after each sampling timepoint and log-transformed titers at baseline. GMR will be calculated only for participants with valid baseline immunogenicity results.

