# 9.2. Sample size determination

The sample size is based on clinical considerations to inform dose regimen decisions for continued clinical development.

With 18 participants receiving mRNA-CR-04 vaccine in each group, there is a 60.3% probability to observe at least 1 AE if the incidence rate is 5% and 85% probability to observe at least 1 AE if the incidence rate is 10%.

With 16 participants receiving mRNA-CR-04 vaccine in each group (PPS for immunogenicity, 10% unevaluable), and a standard deviation of 0.45 for  $log_{10}$  transformed increase from Day 1, the ratio of the upper limit of a 2-sided 95% CI and the point estimate of GMR is 1.74.

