# 2. STATISTICAL HYPOTHESES

There is no hypothesis testing in this study; all analysis will be performed in a descriptive manner. Means and proportions for different objectives will be computed with their 95% confidence intervals (CIs).

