# 5. SAMPLE SIZE DETERMINATION

The sample size is based on clinical considerations to inform dose regimen decisions for continued clinical development.

With 18 participants receiving mRNA-CR-04 vaccine in each group, there is a 60.3% probability to observe at least one participant with an AE if the incidence rate is 5% and 85% probability to observe at least one participant with an AE if the incidence rate is 10%.

With 16 participants receiving mRNA-CR-04 vaccine in each group (PPS for immunogenicity, 10% unevaluable), and a standard deviation of 0.45 for log10 transformed increase from Day 1, the ratio of the upper limit of a 2-sided 95% CI and the point estimate of GMR is 1.74.

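### The pooled ANCOVA prints only single-group means on the Part A scale; adding dose-versus-placebo and 3 versus 10 µg ratios with 95% CIs would be a cheap improvement

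*SAP*

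**What the plan says.** - **Pooled model.** SAP 4.3.2.1 fits log10 titer on baseline, treatment group and study part, without an interaction. It states that "adjusted GMT will be estimated under Part A condition", and says the same of the adjusted GMR. Results are shown for 3, 10, 30 and 100 µg and pooled placebo. SAP 4.4.1.1 plans the same approach for binding IgG.
- **Code.** All five ESTIMATE rows are group means at Part A. The 3 µg row reads "group 1 0 0 0 0 step 1 0/ cl". No row subtracts one group from another, and because the model has no intercept, the solution table lists group levels rather than differences from placebo.
- **Meaning of GMR.** In both documents it is the fold rise from baseline, not a ratio between groups.
- **Where 3 µg is given.** Only in Part B (SAP Table 4). The 10 µg dose and placebo are the only groups in both parts.
- **Other outputs.** SAP 4.1.1 and Protocol 9.4.2.2 also plan separate Part A and Part B summaries, so 3 µg, 10 µg and placebo appear side by side within Part B. A second ANCOVA on the GMR uses dose as a continuous variable.
- **Purpose.** Protocol 4.2 says the repeated 10 µg group may help place 3 µg relative to the earlier Part A groups.

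**The concern.** Protocol 9.2 says the sample size is meant "to inform dose regimen decisions for continued clinical development". That use is comparative: where 3 µg stands against 10 µg and the higher doses, and how far each dose moves beyond placebo. The pooled model is the only analysis that links 3 µg to all the other groups, yet it prints five separate means and leaves the reader to form the comparisons.

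The printed intervals are poorly suited to that. The 3 µg mean reaches the Part A scale by adding a part effect estimated from 10 µg and placebo, so its interval includes the error of that step. The pooled 10 µg and placebo means include a share of the same error. In a difference, much of it cancels, but a reader with only the two intervals cannot see this and will judge the comparison less precise than it is.

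**Working it through.** **The plan's own figure.** SAP 5 assumes 16 evaluable per vaccine group "and a standard deviation of 0.45 for" the log10 increase, and concludes that "the ratio of the upper limit of a 2-sided 95% CI and the point estimate of GMR is 1.74". Check: 10^(t(0.975, 15) × 0.45/√16) = 10^(2.131 × 0.1125) = 1.74. It reproduces.

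**Inputs for the pooled model**
- SD 0.45 (SAP 5), taken as the residual SD. This is an assumption, since the ANCOVA residual SD is not given.
- Evaluable n: 16 per vaccine cell (SAP 5). Placebo is assumed to be 16 of 18 in Part A and 5 of 6 in Part B, applying the same 10% loss.
- Baseline balanced across groups (assumption).
- N = 5 × 16 + 16 + 5 = 101. With five groups, part and baseline, df = 101 − 7 = 94 and t = 1.986. The CI factor is 10^(t × SE).

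**Part effect (A minus B).** Information from 10 µg is 16 × 16/32 = 8, and from placebo 16 × 5/21 = 3.81. Variance = 0.45²/11.81 = 0.01715; SE 0.131.

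**Group means on the Part A scale.** Each equals the group's overall mean plus (its share of participants in Part B) × (part effect). The share is 1 for 3 µg, 1/2 for 10 µg, 5/21 for placebo, and 0 for 30 and 100 µg.
- 3 µg: 0.2025/16 + 0.01715 = 0.0298; SE 0.1726, factor 2.20. In its own part: SE 0.1125, factor 1.67. The part effect is 0.01715/0.0298 = 58% of the variance.
- 10 µg: 0.2025/32 + 0.25 × 0.01715 = 0.0106; SE 0.1030, factor 1.60.
- Placebo: 0.2025/21 + (5/21)² × 0.01715 = 0.0106; SE 0.1030.
- Covariance of 3 µg with 10 µg: 0.5 × 0.01715 = 0.00857 (correlation 0.48). With placebo: (5/21) × 0.01715 = 0.00408 (correlation 0.23).

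**Contrasts**

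| Contrast | SE from model (factor) | SE if treated as independent (factor) | Excess |
|---|---|---|---|
| 3 vs 10 µg | √(0.0298 + 0.0106 − 0.0171) = 0.1525 (2.01) | √(0.0298 + 0.0106) = 0.2010 (2.51) | 32% |
| 3 µg vs placebo | √(0.0298 + 0.0106 − 0.0082) = 0.1796 (2.27) | 0.2010 (2.51) | 12% |
| 3 vs 30 or 100 µg | 0.2061 (2.57) | 0.2061 (2.57) | none |

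Judging 3 versus 10 µg by whether the pooled intervals overlap is stricter still: separation needs 2.20 × 1.60 = about 3.5-fold, against 2.01-fold for the direct interval to exclude 1.

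**Part B alone.** For 3 versus 10 µg, SE = 0.45 × √(2/16) = 0.159, factor 2.11 on 30 df. That is 0.159/0.1525, about 4% wider than the pooled contrast. For 3 µg versus placebo (16 against 5), SE = 0.231, factor 3.04, against 0.1796 pooled.

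**Sensitivity.** The SE ratios do not involve the SD. For SD 0.30 to 0.60, the direct 3 versus 10 µg factor runs from 1.59 to 2.53. With all 114 participants evaluable, the 3 µg factors are 2.10 (Part A scale) and 1.62 (own part), and the 3 versus 10 µg excess is 0.1887/0.1436, or 31%.

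**Dependence on additivity.** Suppose the 10 µg cell in Part A alone is shifted by d on the log10 scale. The part effect moves by (8/11.81)d = 0.68d. Pooled 3 versus 10 µg then moves by −0.5d + 0.5 × 0.68d = −0.16d, and 3 µg versus placebo by (16/21) × 0.68d = 0.52d. Both pooled contrasts, not only those against 30 and 100 µg, rely on no dose-by-part interaction.

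**The case against.** Four points on the other side have weight.

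1. **The comparison can be made elsewhere.** A reader might infer that 3 µg is seen only by extrapolation and that 3 versus 10 µg must be read from distorted intervals. The documents do not support this. In the separate Part B tables the two groups are concurrently randomised and independent, so their SEs combine correctly at 0.159. The 32% arises only when the pooled intervals are compared as if independent, which the SAP nowhere instructs. What remains is that those tables print no ratio and cannot reach 30 or 100 µg.
2. **Nothing printed is wrong.** It is tempting to call the wide 3 µg interval misleading. It is a valid interval for the 3 µg mean on the Part A scale under the additive model, and that placement is the aim in Protocol 4.2. The misreading errs towards too much uncertainty.
3. **No estimand asks for a contrast.** SAP Table 2 gives per-group summary measures, and SAP 2 says "There is no hypothesis testing in this study; all analysis will be performed in a descriptive manner". So the omission does not breach the plan's objectives. But a ratio with a CI is an estimate, not a test, and fits a descriptive plan.
4. **Between-dose information exists in the linear-dose model.** True, but it is a slope that assumes linearity in µg from 0 to 100 and covers only the GMR from baseline. It is not a ratio between two named groups.

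**Conclusion.** The point stands as a cheap improvement, not as an error in the plan. No between-dose or dose-versus-placebo ratio with a CI is produced, and the pooled single-group intervals are a poor substitute wherever the part effect is shared: the implied SE is 32% too large for 3 versus 10 µg and 12% too large for 3 µg versus placebo. For 3 versus 30 or 100 µg the separate SEs combine correctly, so there the loss is only the missing direct estimate. For 3 versus 10 µg the Part B tables already support a comparison nearly as precise as the pooled contrast. The larger gains from the added rows are the placebo comparison and the link to the higher doses.

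The percentages rest on the assumed evaluable numbers and balanced baseline, not on the SD. The CI factors also rest on a residual SD of 0.45. The pooled contrasts themselves rest on an additive part effect.

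**What to change.** - In the pooled model of SAP 4.3.2.1, add ESTIMATE rows with confidence limits for 3, 10, 30 and 100 µg each versus placebo and for 3 versus 10 µg; 3 versus 30 and 3 versus 100 µg are optional. Back-transform to GMT ratios with 95% CIs and label them descriptive. The part term cancels, so the ratios do not depend on the reference part. One set serves both GMT and GMR, because subtracting baseline changes only the baseline slope.
- Report 3 versus 10 µg from Part B alone beside the pooled ratio, as a check that does not borrow from Part A.
- State that every pooled contrast, including 3 versus 10 µg and 3 µg versus placebo, assumes no dose-by-part interaction.
- Keep the existing rows. If wanted, carry the same ratios to the IgG model in SAP 4.4.1.1.

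**Cost.** A few code lines and added table space; no new data. The downside is more intervals without multiplicity control: five contrasts × three post-dose timepoints × two strains = 30, plus 3 × 2 = 6 for the Part B check, before any IgG.

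### The SAP's first PROC MIXED block does not guarantee that the adjusted GMT and GMR rows carry the right dose labels

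*SAP*

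**What the plan says.** SAP Section 4.3.2.1 presents the SAS code as what will be run for GMT and GMR from baseline. The relevant pieces are:

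- A PROC SORT by `group` and `step`, with the comment "group will be sorted with order of Placebo, 3, 10, 30, 100".
- The procedure call "proc MIXED data=study", with no ORDER= option.
- The CLASS statement, beginning "class group (ref='Placebo') step (ref='1". REF= puts Placebo last among the groups and step 1 (Part B, according to the code comment) last among the steps.
- The model "model LOGVAL = BASE group step/ solution noint".
- Five ESTIMATE rows. Row 3 uses "group 1 0 0 0 0 step 1 0/ cl", row 10 uses "group 0 1 0 0 0 step 1 0/ cl", row 30 uses "group 0 0 1 0 0 step 1 0/ cl" and row 100 uses "group 0 0 0 1 0 step 1 0/ cl". The Placebo row puts its 1 in the fifth group position.

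The text of the section says that adjusted values are estimated under the Part A condition and displayed for 3, 10, 30 and 100 µg and pooled placebo. The SAP does not give the type, format or padding of `group`, and it does not mention level ordering.

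**The concern.** The coefficients carry no level names, so each row reports whichever dose occupies that position in the procedure's own level list. The author evidently relied on the sort order with the reference moved to the end, but nothing printed makes the procedure use data order. If the two orders differ, the program returns valid estimates and confidence limits under the wrong dose, and the code contains no check on this.

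The affected outputs are the adjusted GMT and GMR for two strains (vaccine-encoded and WT) at three post-vaccination timepoints (Day 15, Day 31, Month 6). That is 2 × 2 × 3 = 12 sets of rows, all for secondary endpoints. SAP Section 4.4.1.1 plans the same pooled ANCOVA for binding IgG against ten spike antigens, so reusing the code would carry the problem there. Protocol Section 2.1 makes immunogenicity one of three grounds for taking a construct and dose forward, and SAP Section 5 ties the sample size to dose regimen decisions. Dose labels therefore matter in this study.

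**Working it through.** **The plan's own figure.** The SAP gives no number for level order. Its one figure for the GMR analysis is the ratio of upper limit to point estimate in Section 5: 10^(t(0.975, 15 df) × 0.45/√16) = 1.737, which agrees with the stated 1.74. The point below does not depend on it.

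**Inputs from the SAP.** Label-to-position map: 3 → 1, 10 → 2, 30 → 3, 100 → 4, Placebo → 5. Sort order in the comment: Placebo, 3, 10, 30, 100. REF= moves Placebo to the end. No ORDER= option.

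**Assumptions not in the documents.** (a) Without ORDER=, PROC MIXED orders class levels by formatted value. (b) The coding of `group`, which is varied below.

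**Step 1: order required.** Matching each label to its position gives 3, 10, 30, 100, Placebo. This is the commented sort order with Placebo moved last.

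**Step 2: what the sort comment implies about coding.** Plain character values sort as 10, 100, 3, 30, Placebo, so the comment cannot be true of them. Zero-padded or right-justified character doses would sort before the letter P, so Placebo would come last, not first. The comment therefore points to a numeric code with a format, and REF= then names the formatted value.

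**Step 3: order under assumption (a).** Level labels are sorted as text, Placebo is moved last, and the ESTIMATE positions are applied.

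| Labels of `group` | Level order | Rows wrong |
|---|---|---|
| Plain (3, 10, 30, 100), with or without a unit suffix | 10, 100, 3, 30, Placebo | 4 |
| Two-digit padding (03) | 3, 10, 100, 30, Placebo | 2 (30 and 100 swapped) |
| Three-digit padding (003) | 3, 10, 30, 100, Placebo | 0 |
| Right-justified | 3, 10, 30, 100, Placebo | 0 |

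With plain labels, row 3 reports 10 µg, row 10 reports 100 µg, row 30 reports 3 µg and row 100 reports 30 µg.

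**Step 4: illustration.** One data set was simulated with the planned group sizes, a residual SD of 0.45 on the log10 scale, and assumed true GMRs of 1, 3, 5, 8 and 12 for Placebo, 3, 10, 30 and 100 µg. The no-intercept ANCOVA was fitted and the ESTIMATE vectors applied by position.

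| Row label | Levels in data order | Levels in default order, plain labels |
|---|---|---|
| 3 | 3.22 | 4.25 |
| 10 | 4.25 | 13.06 |
| 30 | 8.21 | 3.22 |
| 100 | 13.06 | 8.21 |
| Placebo | 0.84 | 0.84 |

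The four dose estimates are the same numbers in both columns, attached to different labels. The row labelled 10 is overstated by a factor of 13.06/4.25 = 3.1. These values depend on the assumed GMRs and only show the mechanism.

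**Step 5: would ORDER=DATA repair it?** If the sort really yields Placebo, 3, 10, 30, 100, the levels become 3, 10, 30, 100, Placebo and all five rows are right. If `group` held plain character values, the sort itself would give 10, 100, 3, 30, Placebo. ORDER=DATA would preserve that order, and all four dose rows would stay wrong.

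**Step 6: what is not touched.** Placebo is last under every coding. `step` has two levels with step 1 last, so `step 1 0` selects Part A. The second PROC MIXED block uses dose as a continuous variable. The unadjusted GMT and GMR tables and charts do not use this code.

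**The case against.** The strongest reply is that the mechanism needs two facts the documents do not contain: the procedure's default ordering and the coding of `group`. The intent is also clear, since the text names the display groups, the comment gives the order and every ESTIMATE row is labelled. A competent programmer may use padded or ordered labels and never meet the problem. The unadjusted GMTs and GMRs by treatment, planned separately, would probably expose a full permutation. All analyses are descriptive, and no model, population or estimand is wrong.

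Most of this stands. It limits the point to a missing guarantee in the code and brings the priority down. It does not remove the point. The sort comment excludes plain character values, and the coding that most naturally fits it, a numeric code with ordinary labels, is one that permutes all four dose rows under the assumed default. The SAP plans no comparison of adjusted with unadjusted results by dose, so detection is left to chance.

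A reader might go further and infer that the adjusted results will be mislabelled, or that adding ORDER=DATA cures the code by itself. The documents support neither. Some codings give no error, and ORDER=DATA helps only if the sort delivers the commented order.

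**Conclusion.** The point holds as a conditional one. The first PROC MIXED block in SAP Section 4.3.2.1 is correct only under a level order that it does not enforce and a coding of `group` that it does not state. Assuming default ordering by formatted value, between 0 and 4 of the four dose rows carry the wrong label: 4 with plain format labels, 2 with two-digit padding, and none with three-digit padding or right-justified labels. If the default were data order and the sort comment held, no row would be wrong.

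It should be corrected before the code is run, because the failure would be silent and would concern dose. It does not undermine the design, the model or the descriptive results, and it is not evidence that any reported estimate is wrong.

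**What to change.** In SAP Section 4.3.2.1:

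1. State that `group` is an ordered numeric code (Placebo, 3, 10, 30, 100) with a format that supplies the labels.
2. Add ORDER=DATA to the PROC MIXED statement after the sort, or use ORDER=INTERNAL. Alternatively, replace the positional coefficients with non-positional ESTIMATE syntax that names each level, keeping the Part A condition and the same baseline value.
3. Require a check of the printed class-level table against the ESTIMATE labels, and a comparison of adjusted with unadjusted GMTs by dose.
4. Apply the same changes if the code is reused for the IgG ANCOVA in Section 4.4.1.1.

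The cost is a few lines of SAP text and code and one routine output check. Data collection, sample size and the model stay as they are.
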